8.2 Secondary study parameter(s)

SADT-c

To determine whether bronze model SADT-a is predictive for SAD in COPD, the steps described in section 8.1 will be followed. The AUC, LR+ and sensitivity and specificity will be calculated and reported.

To assess the agreement between SADT-c and disease parameters, the steps described in section 8.1 will be reported. Logistic regression analysis results will be reported.

To assess the content validity and reliability of the SADT-c, 10-15 patients with COPD and SAD will be invited for a cognitive interview. Results will be presented in a descriptive way.

To evaluate how SADT-c and SADT-a compare in detecting SAD in COPD the predictive values of the various SADT-c and SADT-a models will be compared.

In case the SADT-c has a significantly reduced predictive value as compared to the SADT-a, new items derived from the cognitive interviews will be added, if any. The amended questionnaire will subsequently be reinvestigated using the same protocol, in the same population (ie. 100 patients with COPD participating in the SCOOP study).

Oscillometry vs spirometry

To assess the agreement between oscillometry and spirometry, triage diagnoses as determined by the expert panel will be compared. Cohen's kappa or comparable statistics will be used to compare the outcomes. Additional analysis will be done adjusted for difficulty of diagnosis and the agreement between panel members. In addition, subgroup analysis will be performed based on the level of agreement between panel members.

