The SADT-a predicts SAD in patients with asthma using a single criterion – wheezing at rest – along with certain basic patient characteristics, such as age, sex, age at diagnosis, and Body Mass Index (BMI); this is the bronze model (area under receiver operation characteristic curve (AUC) 0.74 and positive likelihood ratio (LR+) 2.3). Its ability to accurately identify SAD in asthma is greatly enhanced with the use of spirometry, which evaluates lung function by measuring air volume and flow during breathing; this represents the silver model (AUC 0.87, LR+ 5.0). The results from spirometry primarily include the FEV_1 % predicted. The diagnostic precision further improves with the incorporation of oscillometry, marking the gold model (AUC 0.96, LR+ 12.8). This technique assesses lung function by measuring airflow resistance and includes parameters like the resistance difference between 5 and 20 Hz (R5-R20) and reactance area (AX)⁸.

The current study aims to adapt the original 63-item SADT questionnaire for dedicated use in COPD by reducing the number of items and enhance its efficiency in identifying SAD in individuals with COPD (the SADT-c). This process will follow the approach previously used for asthma⁸. We will assess the predictive value of SADT-c. Additionally, we will determine whether the bronze model of SADT-a is similarly predictive for SAD in COPD as is the bronze model of SADT-c.

Since oscillometry is not standardized in clinical practice, and the access and quality of spirometry is low¹¹, it would be of great value to determine whether oscillometry and spirometry are equally effective in the diagnostic work-up of respiratory symptomatic patients in primary care. Spirometry requires collaboration of the patient to perform a forced expiratory maneuver and well-trained Version 1.0, 19 April 2024 9 of 27

staff¹², whereas oscillometry is easy to perform as no training and limited effort of the patient is required (45 seconds of tidal breathing) and limited training of the staff¹³. In order to compare the effectiveness of spirometry and oscillometry, spirometry and oscillometry measurement will be interpreted by a panel of experts to provide a triage diagnosis. The previously developed machine learning AC/DC tool will be used to explore its diagnostic accuracy using oscillometry and spirometry results¹⁴.

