6.1.2 Secondary study endpoints

The secondary endpoints are:

- 1. Predictive value of SADT-a bronze model for SAD in COPD.
- 2. Agreement between SADT-c results and disease parameters.
- 3. Content validity and reliability.
- 4. Relative predictive value of SADT-a versus SADT-c for SAD in COPD defined as R5– R20 > ULN¹
- 5. Agreement between triage diagnoses from oscillometry and spirometry.
- 6. Relative usability of spirometry and oscillometry.

Required variables:

- 1.
- Triage diagnosis of Asthma/COPD service
- SAD status based on oscillometry test (R5-R20)
- SADT question 8
- Patient characteristics (bronze model)
 - o Age
 - o Sex
 - o Height
 - o Body Mass Index (BMI)
 - Age at diagnosis
- 2.
- Triage diagnosis by Asthma/COPD service
- SAD status based on oscillometry test (R5-R20)
- Lung function results

- Asthma/COPD service collected questionnaires and patient characteristics (as described in chapter 5)
- SADT-c variables
- Patient characteristics bronze model
- 3.
- Cognitive interviews
- SADT-c results
- 4.
- Predictive value SADT-a different models
- Predictive value SADT-c different models
- 5.
- Panel expert diagnoses (spirometry)
- Panel expert diagnoses (oscillometry)
- Patient characteristics
- Difficulty to diagnose (scale)
- 6.
- Operator opinion
- Expert interpreter opinion
- Duration of measurement
- Patient burden

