8.1 Primary study parameter(s)

The primary endpoint is the predictive value of SADT-c for SAD in COPD. The statistical hypothesis for the primary objective is that the predictive value of SADT-c is above the lower limit of the confidence interval of predictive value of SADT-a (AUC 0.74, LR+ 2.3 for the SADT-a bronze model). The hypothesis will be tested at a 2-sided significance level of 0.05.

For the analysis of this primary endpoint, the following population is defined:

- All participants that have a prior or novel COPD (triage) diagnosis, and
- Do not have an asthma, asthma-COPD overlap syndrome, missing or other diagnosis, and
- Have filled in the SADT-c questionnaire.

The presence of SAD will be based on oscillometry results. A resistance difference between 5 and 20 Hz (R5-R20) cutoff of 0.07 kPa x s x L⁻¹ will be used to define the presence of SAD¹⁵.

Analysis will be performed as done earlier for the development of SADT for asthma⁸. In short, to assess the predictive value of SADT-c we first will select the most important SADT items (secondary study parameter). Regression analysis will be used to select SADT items that show a relation with SAD in the expected direction based on the content validity of the items. In a next step the most important SADT items for SAD group will be selected by using logistic regression models. Prediction models using bootstrapping resampling will be used. In addition to the individual SADT items, also patient characteristics, such as age, sex, and height, BMI, will be considered as independent predictors in the model.

Selected key SADT items will be used together with available clinical information to build logistic regression models to predict the SAD group. Three levels of clinical information will be considered resulting in three regression models:

- Bronze: Basic patient characteristics (such as age, sex, age at diagnosis, BMI, or other)
- Silver: Spirometry test results (FEV₁ % predicted)
- Gold: Oscillometry test results (R5-R20 and reactance area (AX)).

For each model the area under the receiver operating characteristic curve (AUC), positive likelihood ratio (LR+) and sensitivity and specificity will be calculated, using a probability cut-off of 0.5 to indicate predicted SAD.

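### Section 8.2 evaluates the existing SADT-a bronze model by model-building steps and never says its coefficients stay fixed, so Objective 2 would be answered by a refit

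*Protocol*

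**What the plan says.** The introduction presents SADT-a as a finished tool for asthma. Its bronze model takes wheeze at rest as the one symptom item; the remaining terms are described as follows: "along with certain basic patient characteristics, such as age, sex, age at diagnosis, and Body Mass Index (BMI"). The performance reported for it in asthma is an AUC of 0.74 with an LR+ of 2.3. Objective 2 asks whether this bronze model is predictive for SAD in COPD, and Objective 4 how SADT-c compares with SADT-a.

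For Objective 2, section 8.2 gives one instruction: "To determine whether bronze model SADT-a is predictive for SAD in COPD, the steps described in section 8.1 will be followed". It then asks for AUC, LR+, sensitivity and specificity. The analytic steps in section 8.1, modelled on the earlier development work in asthma, are:

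- item selection: "Regression analysis will be used to select SADT items that show a relation with SAD in the expected direction";
- resampling: "Prediction models using bootstrapping resampling will be used", with no purpose stated;
- model fitting: "Selected key SADT items will be used together with available clinical information to build logistic regression models to predict the SAD group".

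For the SADT-a endpoint, section 6.1.2 requires "SADT question 8" and, under "Patient characteristics (bronze model"), age, sex, height, BMI and age at diagnosis.

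For Objective 4, section 8.2 compares the predictive values of the SADT-c and SADT-a models. If SADT-c is significantly worse, items from the cognitive interviews are added, if there are any.

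**The concern.** Whether an existing model works in a new disease is a question of external validation. The equation is applied as it stands, and its discrimination and calibration are measured. If the coefficients are re-estimated on the same COPD patients, the result is a new COPD model that uses the SADT-a variables. It can look useful when the existing tool is not, because the fit adapts size and sign of every coefficient to the data at hand.

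Two conclusions are at stake. Objective 2 could report that SADT-a predicts SAD in COPD when a clinician using the existing tool would not see that performance. Objective 4 would compare two models fitted to the same patients, with only SADT-c also gaining from a search over items. Any tilt towards SADT-c makes the amendment rule in 8.2 less likely to be triggered.

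**Working it through.** **The plan's own figure.** The only performance figures for SADT-a bronze are AUC 0.74 and LR+ 2.3. They come from asthma patients and cannot be rederived from the protocol. No value for COPD is given.

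**Inputs from the protocol.** Section 4.4: 100 COPD patients and a SAD prevalence of 74% to 83%, so 74 with and 26 without SAD, or 83 and 17. Introduction: one item plus four characteristics, so 1 + 4 = 5 terms. Section 5.1: about 15 SADT-c questions.

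**Assumptions.** Independent normal predictors; an existing score with equal fixed weights, whose true AUC in COPD is set by hand; refitting by logistic regression. AUC is the share of SAD/non-SAD pairs ranked correctly. Optimism-corrected AUC = apparent AUC − mean over resamples of (AUC of the resample's model in the resample − AUC of that model in the original data).

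**Step 1: the score carries no information in COPD (five terms).**

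| With SAD | Unchanged score | Refit, apparent | Refit, corrected |
|---|---|---|---|
| 74 | 0.50 | 0.638 | about 0.54 |
| 83 | 0.50 | 0.663 | about 0.55 |

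Refitting alone adds 0.638 − 0.50 = 0.138 to 0.663 − 0.50 = 0.163. Bootstrap correction removes most of this and leaves about 0.04 to 0.05.

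**Step 2: weak transport, true AUC 0.60 (five or six terms).** The apparent refit averages 0.67 to 0.70. It reaches the asthma value of 0.74 or more in 9% to 25% of runs.

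**Step 3: coefficients that point the wrong way in COPD, true AUC 0.26.** The refit reports 0.77 to 0.79 apparent and 0.71 to 0.73 after correction. Bootstrapping removes overfitting from the refitted model; it does not examine the original coefficients, so it cannot show that they failed.

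**Step 4: precision of an unchanged score.** By Hanley and McNeil, with A the AUC, Q1 = A/(2 − A) and Q2 = 2A²/(1 + A):

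SE² = [A(1 − A) + (n1 − 1)(Q1 − A²) + (n0 − 1)(Q2 − A²)]/(n1·n0).

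At A = 0.74 the SE is 0.052 for 74/26 (95% CI about 0.64 to 0.84) and 0.058 for 83/17 (about 0.63 to 0.85).

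**Step 5: Objective 4 when nothing predicts SAD.** SADT-c is taken as four characteristics plus the best two of 15 items (an assumed rule), with selection repeated in each resample. Its corrected AUC averages about 0.575 to 0.593.

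- Against the unchanged SADT-a: 0.575 − 0.50 and 0.593 − 0.50, a false gap of about 0.08 to 0.09.
- Against a refitted, corrected SADT-a: 0.575 − 0.54 and 0.593 − 0.55, about 0.035 to 0.04.

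Neither comparison is free of bias; fitting both models in the same patients halves it or better.

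**Step 6: which variables are bronze?** The introduction names five terms, in a list introduced as examples. Section 4.4 counts four variables. Section 6.1.2 lists question 8 plus five characteristics, six in all, with height added. An existing equation cannot be applied until its terms are settled.

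**The case against.** The protocol does not say in so many words that SADT-a is re-estimated. The steps of 8.1 could mean only its population, SAD definition, 0.5 cut-off and accuracy measures, and section 8 is declared a summary with technical detail to follow in the statistical analysis plan. This stands in part: refitting is the natural reading, not the only one. However, 8.2 names the accuracy measures in its own next sentence, and what 8.1 describes as successive steps is selection and model building. Whether an existing model is applied or rebuilt decides which question is answered, so it is more than technical detail.

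Four stronger readings are tempting and are not supported.

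- A reader might infer that items are reselected for SADT-a. Section 6.1.2 fixes question 8, so only the coefficients are open.
- A reader might infer that neither transport nor SADT-c versus SADT-a is tested at all. A comparison is planned, the amendment rule presupposes a test of significance, and 8.1 has a hypothesis against the SADT-a benchmark. The accurate point is that the comparison would not be with SADT-a as it exists, and that the benchmark comes from asthma.
- A reader might take height in 6.1.2 as proof of a different model. The introduction's list is illustrative, and 6.1.2 lists data to be collected; height may serve BMI or the limit of normal.
- A reader might want a firm figure for how often SADT-c would falsely win. That depends on a selection rule the protocol does not fix.

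It can also be argued that refitting both models is a fair comparison of predictor sets. That is correct for Objective 4, as step 5 shows. It does not answer Objective 2.

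**Conclusion.** The point holds for Objective 2: as written, section 8.2 would measure how well the bronze variables can be fitted to SAD in COPD, and nothing in the protocol secures a test of the existing equation. With no true signal, the refit would show an AUC of 0.64 to 0.66 apparent, or about 0.54 to 0.55 corrected, against 0.50 for the unchanged score. With reversed coefficients, a corrected refit could still show 0.71 to 0.73. For Objective 4 the finding is narrower: SADT-c keeps an advantage from being developed in these patients, and this must be reduced and declared because it cannot be removed.

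The sizes rest on the assumed predictor distributions, equal weights and, for step 5, the assumed selection rule. They are illustrative. The conclusion that a refit does not test transport needs none of these assumptions. The change should be made before the analysis plan is finalised.

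**What to change.** 1. In 8.2, replace the reference to the 8.1 steps. For Objective 2, state that the original SADT-a bronze equation, with its original variables, intercept and coefficients, is applied unchanged to the COPD participants. Report AUC with CI, LR+, sensitivity, specificity and calibration.
2. Report an intercept-recalibrated or refitted version separately and label it a model update. Recalibrating the intercept leaves the AUC unchanged but moves the measures taken at the 0.5 cut-off.
3. For Objective 4, estimate a paired AUC difference with CI in the same patients, using bootstrap optimism correction that repeats the SADT-c item selection in every resample. Give the difference against both the unchanged SADT-a and the refitted, optimism-corrected SADT-a. State that a residual advantage for SADT-c remains because it is developed in these patients.
4. Reconcile the bronze variables in the introduction, section 4.4 and section 6.1.2, and say what height is for.

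Cost: wording and a modest amount of extra analysis. The item and characteristics are already required by 6.1.2, so no new participant data should be needed. This assumes that the sponsor can obtain the original equation from reference 8; the protocol does not reproduce it.

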3. STUDY DESIGN

The SCOOP-study will be executed in the Netherlands. The study consists of one visit during which all data will be collected. The aim is to include 200 participants in total. Of the 200 patients that will be seen for a visit, approximately 50 participants with previously diagnosed Chronic Obstructive Pulmonary Disease (COPD) and 150 participants without any diagnosis at the time of the visit will be invited. This should result in a total of 200 participants of which 100 are diagnosed with COPD: 50 with a pre-existing diagnosis and 50 newly diagnosed. An overview of the study flow is presented in figure 1.

Participants will visit the site for their usual care, which can be either a follow-up visit for those with an existing COPD diagnosis or a diagnostic visit. In addition to their usual care participants of the study will be asked to complete an oscillometry measurement and a Small Airway Dysfunction Tool for COPD (SADT-c) questionnaire. A panel of international experts will then review the oscillometry and spirometry reports of all 200 participants. Each report will be assessed by 3 to 5 independent pulmonologists in a randomized order. Finally, the triage diagnoses derived from oscillometry and spirometry assessments will be compared. The answers to the SADt-questionnaire items will be compared to the patients' respective SAD status to determine predictive value of SADT-c. Furthermore, ten to fifteen patients with COPD and SAD will be asked to participate in a cognitive interview to assess patient comprehension and necessity of additional questions. In case these are required, 100 COPD patients will be asked to complete the amended questionnaire.

[figure not shown]

Figure 1: Study flow for patients

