5.1 Small Airways Dysfunction Tool (SADT) questionnaire

The SADT questionnaire was developed for patients with asthma and consist of 63 items. SADT items were scored on a 3-point scale (no, yes, unknown)¹⁰. The items reflect specific signs and symptoms which could be suggestive for Small Airways Dysfunction (SAD) or could reflect signs and symptoms that are suggestive for less SAD.

A shorter version of the SADT for asthma with items more tailored to COPD patients will be devised as a part of study. Input from the scientific advisory board (in part the steering committee of the ATLANTIS study¹⁸.) and patient interviews (described in chapter 5.4) will be used. The SADT for COPD (SADT-c) will contain approximately 15 questions.

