5.4 Cognitive interviewing

The aim of cognitive interviewing is to assess how participants process information to comprehend, respond to the questions and to determine whether new items are needed to complete the SADT-c.

A total of ten to fifteen patients with COPD and SAD who are native Dutch speakers will be invited to participate in cognitive interviews about the SADT-c with a clinician. Patients are to be representative of the real-world population of patients with COPD as much as possible. The interviewer will report the answers anonymously and will discuss the results of the interviews in a meeting with a member of the GPRI team.

The followings steps will be followed to conduct a cognitive interview:

- The clinician will present a form with the patient-reported version of the questions under study to the patient and will ask the patient to read it and answer the question. The clinician will record the answer.
- **2.** The clinician will ask the scripted questions.
- **3.** The clinician will investigate whether there are additional items that could describe SAD.
- **4.** The clinician will also report all other issues / comments that were raised during the interview.

The following scripted questions will be asked:

- In your own words, what do you think this question is asking?
- Was this question easy to understand? Are there any specific words that are difficult to understand?
- Was there anything else about the question that was unclear to you?
- Suppose you would be talking with others about /question/, which word or phrase would you use?
- Is there anything else you would like to share about this question?

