6.2 Study procedures

Participants will be invited by the study site for a diagnostic or control visit to perform a lung function test. Together with the invitation for this visit, information about the SCOOP study is sent. The recipient will have the option to make their interest or disinterest in the study known before their visit (but this is not required). The study flow is presented in document E₃.

During the regular diagnostic or control visit participants that did not reply to the initial information and participants that have shared their interest will be further informed about the SCOOP study and asked whether they would like to participate. In case a person does not want to participate in the study, the Asthma/COPD visit will continue as usual. In case a person does want to participate in the study, the study activities will be added to the regular visit.

After signing informed consent, the visit will include a (pre-)oscillometry measurement followed by a (pre-)spirometry measurement. In case of a diagnostic visit the participant will use Salbutamol followed by a post-oscillometry and post-spirometry measurement after a 15-minute wait time. During the wait time, or after the measurements in case of a control visit, the participant is asked to fill in the SADT-c questionnaire and two additional study questions.

10-15 participants with a triage diagnosis of COPD and SAD status defined as R5–R20 > ULN will be invited for a cognitive interview regarding the new SADT-c questionnaire. Purposeful sampling will be used, to have a widespread of patient characteristics. If new items are added to the SADT-c questionnaire as a result of the cognitive interviews, 100 COPD patients that had previously completed the SADT-c questionnaire will be asked to complete the updated questionnaire.

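### Section 8.2 assigns reliability of the SADT-c to 10-15 descriptive cognitive interviews designed to test comprehension and content, and no reliability analysis is stated

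*Protocol*

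**What the plan says.** The third secondary endpoint in Protocol section 6.1.2 is "Content validity and reliability", and the objectives table in the Summary repeats it under the aim of developing the SADT-c. Section 6.1.2 lists two inputs for it: the cognitive interviews and "SADT-c results".

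Section 8.2 gives the analysis: "To assess the content validity and reliability of the SADT-c, 10-15 patients with COPD and SAD will be invited for a cognitive interview". It then adds: "Results will be presented in a descriptive way". It names no coefficient, no comparison and no use of the questionnaire data for this endpoint.

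Section 5.4 sets out what the interviews are for: "The aim of cognitive interviewing is to assess how participants process information to comprehend, respond to the questions", and to find out whether items are missing. The scripted questions ask about meaning, difficult words, unclear points and preferred phrasing.

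On the chance of repeated answers, section 3 says "The study consists of one visit during which all data will be collected". Section 6.2 allows a second completion only if the interviews lead to new items: "100 COPD patients that had previously completed the SADT-c questionnaire will be asked to complete the updated questionnaire".

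**The concern.** Content validity and reliability are different properties. Content validity asks whether the items are understood and cover the right ground, and cognitive interviews are a proper way to study it. Reliability asks how far answers are reproducible, or how far items agree with one another. It needs an estimate built from repeated answers or from the relation between items, with a statement of its precision.

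Section 8.2 joins the two under one method that suits only the first. If it is followed, the study could report that reliability was assessed with no estimate behind the statement. That matters for a questionnaire meant for clinical practice, where readers will take such a statement at face value.

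**Working it through.** **Step 1. Is a reliability analysis stated anywhere?** The places that could hold one are:

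| Protocol section | Content | Reliability analysis of the SADT-c? |
|---|---|---|
| Summary, 6.1.2 | Endpoint named; interviews and questionnaire results listed as inputs | No |
| 5.4 | Interview aim, steps and script | No; comprehension and missing items |
| 8.1 | Item selection and prediction models | No |
| 8.2, SADT-c | Interviews, reported descriptively | Named, with no analysis |
| 8.2, oscillometry vs spirometry | Kappa for triage diagnoses | No; a different question |

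The protocol gives no reliability figure, target or sample-size basis, so there is nothing to reproduce.

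**Step 2. What could the interviews yield?** Under section 6.2, interviewees are participants who already have a COPD triage diagnosis and a SAD status, and who are asked to complete the SADT-c at the visit. In the first interview step of section 5.4 the patient answers the question again and the clinician records the answer. So two answers per item would normally exist for 10 to 15 people.

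Suppose these were used for a test-retest coefficient of a total score, with two administrations and a one-way intraclass correlation r. The value of r is my assumption, taken from 0.7 to 0.9. With F = (1 + r)/(1 − r):

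- Lower limit: (F_L − 1)/(F_L + 1), where F_L = F / F₀.₉₇₅(n−1, n)
- Upper limit: (F_U − 1)/(F_U + 1), where F_U = F × F₀.₉₇₅(n, n−1)

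Example, r = 0.8 and n = 10: F = 1.8/0.2 = 9. F_L = 9/3.78 = 2.38, so the lower limit is 1.38/3.38 = 0.41. F_U = 9 × 3.96 = 35.7, so the upper limit is 34.7/36.7 = 0.95.

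| Assumed r | 95% CI, n = 10 | 95% CI, n = 15 |
|---|---|---|
| 0.7 | 0.20 to 0.91 | 0.32 to 0.89 |
| 0.8 | 0.41 to 0.95 | 0.51 to 0.93 |
| 0.9 | 0.67 to 0.97 | 0.74 to 0.96 |

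At 0.7 or 0.8 the interval spans poor to excellent reliability. All interviewees also have SAD, so their scores cover a restricted range.

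**Step 3. What could the data already collected yield?** Section 5.1 says: "The SADT for COPD (SADT-c) will contain approximately 15 questions". Section 3 expects about 100 participants with COPD. For internal consistency α with k = 15 items and n = 100, the Feldt interval is

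1 − (1 − α) × F₀.₉₇₅(n−1, (n−1)(k−1)) to 1 − (1 − α) × F₀.₀₂₅(n−1, (n−1)(k−1)).

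The degrees of freedom are 99 and 99 × 14 = 1386, and the F values are 1.312 and 0.735.

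- α = 0.7: 1 − 0.3 × 1.312 = 0.61 to 1 − 0.3 × 0.735 = 0.78
- α = 0.8: 0.74 to 0.85
- α = 0.9: 0.87 to 0.93

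Bonett's approximation at α = 0.7 gives 0.60 to 0.78, so the choice of interval hardly matters. Again α is assumed. The questionnaires could give a usable estimate of one aspect of reliability, but the protocol states no such analysis.

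**The case against.** Three arguments on the other side deserve an answer.

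**The interviews do produce repeat answers.** A reader might infer that each interviewee answers only once, so that reliability could not be estimated from the interviews at any sample size. The documents do not support that. Sections 5.4 and 6.2 together imply an answer at the visit and another at the interview, and the two inputs in section 6.1.2 fit a comparison of these. This part of the objection stands. What remains is that no comparison is stated, the number is 10 to 15, and section 5.4 has the interviewer report answers anonymously, which may prevent linking them to the visit.

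**The choice of coefficient belongs in the analysis plan.** Section 8 calls itself a summary and promises a more technical plan before database lock. Had section 8.2 left reliability open, that would settle the matter. Instead it assigns a method and a form of reporting. A plan that merely elaborated this text would still contain no reliability estimate.

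**The consequence is small, and the obvious remedy is imperfect.** Reliability has no hypothesis or threshold, and the rule in section 8.2 for amending the questionnaire turns on predictive value. Internal consistency is also an awkward fit. Items are answered no, yes or unknown, some point towards SAD and others away from it, and selection may leave very few; the asthma bronze model kept a single one. All of this stands. It limits the remedy, and it is why deleting the word is an equally acceptable fix.

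**Conclusion.** The point holds in a limited form. Section 8.2 says the interviews assess reliability, section 5.4 describes them as a study of comprehension and content, and no section states a reliability analysis. Even if the visit and interview answers were compared, 10 to 15 patients would give an interval such as 0.41 to 0.95 or 0.51 to 0.93 at an assumed coefficient of 0.8. The plan as written cannot support a conclusion on reliability.

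The mismatch between sections rests on the text alone. The intervals rest on assumed coefficients of 0.7 to 0.9, two administrations and, for internal consistency, 15 scored items in 100 patients. They show precision only and predict nothing about the SADT-c.

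The defect touches part of one of six secondary endpoints and leaves the primary analysis unaffected. It should be corrected because the change is cheap.

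**What to change.** In section 8.2, and to match in section 6.1.2 and the Summary, limit the cognitive interviews to content validity. Then do one of the following.

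1. **Delete reliability from the endpoint.** This costs only wording.
2. **Define it and report it descriptively with confidence intervals, from data already collected:**
   - internal consistency of the SADT-c items in the roughly 100 COPD questionnaires, with items scored in a common direction and a stated rule for unknown answers;
   - only if the amended questionnaire is given, item-level agreement for the unchanged items, which the same patients will then have answered twice.

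Option 2 needs no new patients or visits beyond those planned, and only a small extra analysis. Its limits should be stated with the result. Internal consistency is a partial measure for a set of predictors and does not apply if the final tool keeps a single item. Agreement between the two completions would be supportive only, because the questionnaire has changed and the interval between completions is not fixed.

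### The protocol gives conflicting triggers for amending SADT-c, re-fits any amended version in its own development patients, and does not say which version answers the primary hypothesis

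*Protocol*

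**What the plan says.** **Primary hypothesis (protocol 8.1).** The claim to be tested is that "the predictive value of SADT-c is above the lower limit of the confidence interval of predictive value of SADT-a". The benchmark is given as point estimates only ("AUC 0.74, LR+ 2.3 for the SADT-a bronze model"); the confidence limit itself is not stated. On the error rate: "The hypothesis will be tested at a 2-sided significance level of 0.05".

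**Amendment according to 8.2.** After the comparison of SADT-c with SADT-a: "In case the SADT-c has a significantly reduced predictive value as compared to the SADT-a, new items derived from the cognitive interviews will be added,". This applies only where the interviews have produced such items. On the re-test, 8.2 says: "The amended questionnaire will subsequently be reinvestigated using the same protocol, in the same population", which it identifies as the 100 COPD patients of this study.

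**Amendment according to the summary and sections 3 and 6.2.** In the summary and section 3, the cognitive interviews judge whether further questions are needed; if so, the COPD patients complete the amended questionnaire. Section 6.2 reads: "If new items are added to the SADT-c questionnaire as a result of the cognitive interviews, 100 COPD patients that had previously completed" SADT-c will be asked to fill in the new one. None of these places sets an accuracy condition. Section 5.1 adds that input from the same interviews helps to shape SADT-c itself.

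**Timing and source of items.** Section 3 states: "The study consists of one visit during which all data will be collected". Section 6.2 draws the 10-15 interviewees from participants already classified as having COPD with SAD.

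**The concern.** The protocol describes two procedures for the same event. If the interviews yield new items but SADT-c is not significantly worse than SADT-a, sections 3 and 6.2 call for re-completion and 8.2 does not.

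Whichever trigger applies, the amended tool is assessed under weak conditions:

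- It is fitted again in the patients from whom it was developed, with more candidate items.
- The people who proposed the items answer them again, and they all come from the SAD group.
- Symptoms reported later are set against R5-R20 measured at the earlier visit.

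Because no section names the version that answers the primary hypothesis, the reported predictive value of SADT-c could come from either. At stake are an optimistic AUC for the amended tool and, depending on the trigger, the error rate of the primary claim.

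**Working it through.** **1. The triggers side by side.**

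| Interviews yield items | SADT-c significantly worse | Summary, 3 and 6.2 | 8.2 |
|---|---|---|---|
| yes | yes | re-complete | re-complete |
| yes | no | re-complete | no action |
| no | either | no action | no action |

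The second row is the conflict.

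**2. The plan's own error rate.** One test at two-sided 0.05 gives 0.05, as stated. Two unadjusted tests, if independent, give 1 - 0.95² = 0.0975. For the favourable tail alone, 1 - 0.975² = 0.0494 instead of 0.025. Tests in the same patients are correlated, and a re-fit is biased upward, so these values are only a reference. A simulation is more informative.

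**3. Simulation inputs.** From section 4.4: 100 COPD patients and SAD prevalence 74% or 83%, hence 26 or 17 patients without SAD. From 8.1: AUC 0.74. Assumed, because the protocol does not give them:

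- SADT-a lower limit L of 0.65, 0.68 or 0.70, with the true AUC of the visit SADT-c equal to L.
- 1, 3 or 5 added yes/no items unrelated to SAD.
- Success if (AUC - L)/SE > 1.96, with the Hanley-McNeil SE.
- 8.2 trigger if (0.74 - AUC)/SE > 1.96, treating 0.74 as fixed.
- Interview trigger: re-test whatever the first result, with either version allowed to count.

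The re-test is a logistic re-fit in the same patients and gives an apparent AUC without bootstrap correction. There were 2,000 runs per setting.

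**4. Results (range over L and prevalence).**

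| Noise items added | AUC rise when 8.2 trigger fired | AUC rise over all runs | False success, interview trigger |
|---|---|---|---|
| 1 | 0.02-0.04 | 0.01-0.02 | 0.07-0.10 |
| 3 | 0.05-0.09 | 0.03-0.05 | 0.13-0.18 |
| 5 | 0.08-0.12 | 0.05-0.08 | 0.19-0.30 |

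False success at the first test was 0.047-0.076. It exceeds 0.025 because the SE is approximate with only 17-26 patients without SAD. With the 8.2 trigger it became 0.047-0.085 overall, and the largest rise within one setting was 0.010 (0.075 to 0.085). The re-test then starts from a low AUC, so a biased gain seldom carries it past the bar.

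**5. How large a deficit fires the 8.2 trigger.** At AUC 0.74 the Hanley-McNeil SE is 0.052 (74/26) to 0.058 (83/17). If both tools are measured in the same patients with correlation r between their AUCs (0.3-0.7 assumed), the SE of the difference is SE × √(2(1 - r)):

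- r = 0.7: 0.052 × 0.775 = 0.040; × 1.96 = 0.08.
- r = 0.3: 0.058 × 1.183 = 0.069; × 1.96 = 0.135.

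The trigger therefore needs an observed deficit of about 0.08-0.13 and would miss moderate underperformance.

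**6. Share of interviewees.** They make up 10/83 = 12% to 15/74 = 20% of the expected SAD group, and none of the non-SAD group if SAD is classified as in section 6.2.

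**The case against.** A reader might infer that a SADT-c which fails its primary test is enlarged and re-tested until it passes. The documents do not support that. The 8.2 trigger follows the secondary comparison of the two tools and is not the primary test. An observed AUC of 0.70 with an assumed limit of 0.65 would miss the primary bar (0.05 is less than 1.96 × 0.052 = 0.10), yet a deficit of 0.04 against 0.74 would not fire the trigger. Conversely, if the comparator is SADT-a in these COPD patients, SADT-c could clear the bar and still fire it; the protocol does not say which comparator is meant. No section states that the amended result replaces the primary one.

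Nor do the figures support a large error inflation under 8.2. Re-testing whenever the AUC merely falls short of a bar would inflate it more, but the protocol contains no such rule.

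Three further points have weight:

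- **Bootstrap.** Section 8.1 plans bootstrap resampling, which can reduce optimism within one model. It does not cover a result-driven amendment unless that step is resampled too.
- **SAP.** It could name the confirmatory version. But the re-test in the same patients and the conflicting triggers are protocol procedures.
- **Sequence.** Section 6.2 alone can be read as following from 8.2. Section 3 and the summary are harder to read so, because they tie the need for items to the interviews.

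**Conclusion.** The point holds as a contradiction between sections and as a limit on what the amended tool can show. The summary and sections 3 and 6.2 must be reconciled with 8.2, and the protocol must say which version is primary.

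Optimism in the amended tool's apparent AUC is the main harm under the 8.2 trigger: about 0.02-0.12 for 1 to 5 noise items. False success there is nearly unchanged. Under the interview trigger it could reach about 0.07-0.30, but only if either version may count as the primary result, which the protocol neither states nor excludes. The choice of trigger therefore matters.

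These sizes rest on the assumed lower limit, the assumed number of items, items with no information, and AUCs without bootstrap correction. The effects of the time gap and of the interviewees' repeat answers were not quantified.

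**What to change.** - State one trigger in the summary and sections 3, 6.2 and 8.2. Preferably it is interview content, decided before any accuracy result is seen.
- Fix the primary endpoint on the SADT-c completed at the visit.
- Report any amended version as exploratory and in need of validation in new patients. Give the time from oscillometry to re-completion and a sensitivity analysis without the interviewees.
- Adjust the one-visit statement in section 3 to allow for re-completion.

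**Cost.** The changes are to wording, and the current study needs no extra participants or tests. The amended tool could not support the confirmatory claim. An interview-only trigger may also mean re-contacting COPD patients more often than 8.2 would, since 8.2 does so only after a significant deficit.
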